6.4 Efficacy

Efficacy assessments will include:

- Migraine days
- Migraine Physical Function Impact Diary (MPFID)

The timing and frequency of these assessments are outlined in [Table 6-1](#) , [Table 6-2](#), [Table 6-3](#) and [Table 6-4](#). Patients will record the efficacy information using the provided eDiary platform. To aid in compliance, it is recommended that the information be completed at the same time every day that is convenient for the patient. Retroactive completion will be allowed one day

prior to the time of completion. Any entries > 2 days old will not be allowed and will be considered missing data.

During the **COVID-19 pandemic** that limits or prevents on-site study visits, efficacy information including PRO scales may still be collected by using the provided eDiary.

6.4.1 Migraine Days

A migraine day is defined as any calendar day in which the patient experiences a qualified migraine headache (onset, continuation, or recurrence of the migraine headache). A qualified migraine headache is defined as a migraine with or without aura, lasting for ≥ 30 minutes, and meeting at least one of the following criteria:

1. ≥ 2 of the following pain features:
 - Unilateral
 - Throbbing
 - Moderate to severe
 - Exacerbated with exercise/physical activity
2. ≥ 1 of the following associated symptoms:
 - Nausea and/or vomiting
 - Photophobia and phonophobia

If the patient took a migraine-specific medication (ie, triptan or ergotamine) during aura, or to treat a headache on a calendar day, then it will be counted as a migraine day regardless of the duration and pain features/associated symptoms.

To further characterize a migraine day, the following information will be collected:

- Date and time of start of headache (ie, migraine or non-migraine headache)
- Date and time of end of headache
- Worst pain severity per headache
- Pain features (eg, one-sided, throbbing, worsens with exercise/physical activity)
- Symptoms (eg, aura, nausea, vomiting, photophobia, phonophobia)
- Use of acute headache medications (medication name (from pre-entered list), date of dosing, number of times taken of each date, number of units taken)

6.4.2 Migraine Physical Function Impact Diary (MPFID)

Patients will complete the MPFID every day using the eDiary at time points outlined in [Table 6-1](#) , [Table 6-2](#), [Table 6-3](#) and [Table 6-4](#). The recall period is the past 24 hours.

The Migraine Physical Function Impact Diary (MPFID) is a self-administered 13-item instrument measuring physical functioning. It has two domains, Impact on Everyday Activities (7 items) and Physical Impairment (5 items), and one stand-alone global question which provides an assessment of overall impact on everyday activities. Patients respond to items using

a 5-point scale, with difficulty items ranging from “Without any difficulty” to “Unable to do” and frequency items ranging from “None of the time” to “All of the time.”

These are assigned scores from 1 to 5, with 5 representing the greatest burden. For each domain, the scores will be calculated as the sum of the item responses and the sum will be rescaled to a 0 - 100 scale, with higher scores representing greater impact of migraine (ie, higher burden). There will be a score for each of the two domains and a third score for the stand-alone item. Patients with a reduction of 5 or more points in either of the two domains will be evaluated as responders.

6.4.3 Appropriateness of efficacy assessments

The definition of migraine day ([Section 6.4.1](#)) is consistent with the diagnostic criteria of migraine and probable migraine according to the International Classification of Headache Disorder ([ICHD-3](#)). The monthly migraine days will be calculated using migraine day data collected from the eDiary. Migraine days are commonly used as a primary endpoint in pivotal trials as acknowledged both in the IHS guidelines for controlled trials of drugs in migraine ([Tfelt-Hansen et al 2012](#)).

As the mean change in MMD however describes a population-based measure and given the natural variability in migraine trials often is associated with small effect sizes, clinically an important complementary information is the proportion of patients that achieve a certain clinical benefit, which is usually described with achieving at least a 50% reduction of migraine days compared to the individual baseline (“50% responder rate”). In pivotal trials, 50% (or higher) responder rates are usually included as secondary or key secondary outcomes. Given that this trial is not considered a pivotal trial but rather should provide clinical guidance, the 50% RR was considered more relevant as therefore been chosen as the primary endpoint. The change in physical impairment and impact on everyday activities as assessed by the MPFID was selected because they are highly clinically relevant and provide complementary information to the primary endpoint in the evaluation of AMG 334 as a migraine prophylactic agent.

Reduction in acute monthly migraine-specific medication is an important secondary outcome, as many patients with longer-term and very frequent use of rescue medication can potentially develop medication-overuse headache as a complication.

6.5 Safety

Safety assessments will include:

- Adverse events ([Section 7.1](#))
- Physical examination
- Vital signs
- Height/Weight

- Laboratory evaluations
- Pregnancy testing (females of childbearing potential)
- ECG
- Columbia Suicide Severity Rating Scale (C-SSRS) ([Section 7.6](#))

The timing and frequency of these assessments are outlined in [Table 6-1](#) , [Table 6-2](#), [Table 6-3](#) [Table 6-4](#) and [Table 6-5](#).

6.5.1 Physical examination

A complete physical examination will include the examination of general appearance, skin, neck (including thyroid), eyes, ears, nose, throat, lungs, heart, abdomen, back, lymph nodes, extremities, vascular and neurological. If indicated based on medical history and/or symptoms, rectal, external genitalia, breast, and pelvic exams will be performed.

A brief physical exam, as per local practice, will include the examination of general appearance and will be at all visits starting from Visit 2, except where a complete physical examination is required (see above).

Information for all physical examinations must be included in the source documentation at the study site. Clinically relevant findings that are present prior to randomization must be included in the Medical History part of the eCRF. Significant findings made after first administration of investigational drug which meet the definition of an Adverse Event must be recorded on the Adverse Event section of the eCRF.

6.5.2 Vital signs

Vital signs include BP, pulse and temperature measurements. Pulse, systolic and diastolic blood pressure will be measured three times when the patient has been sitting for approximately five minutes. The repeat sitting measurements should be made at approximately 1 - 2 minute intervals and the mean of the three measurements will be used for analysis purposes. If an automated blood pressure device is used, it should be calibrated according to the manufacturer's guidelines. The method to take temperature should be consistent throughout the study.

6.5.3 Height and weight

Height in centimeters (cm) and body weight (to the nearest 0.1 kilogram (kg) in indoor clothing, but without shoes) will be measured.

6.5.4 Laboratory evaluations

A central laboratory will be used for analysis of all specimens collected. Details on the collections, shipment of samples and reporting of results by the central laboratory are provided to investigators in the laboratory manual.

Clinically notable laboratory findings are defined in [Appendix 1](#).

During the **COVID-19 pandemic** that limits or prevents on-site study visits, or if visits by site staff to a patient's home are not feasible, the collection of samples may be modified by Novartis and will be communicated to the Investigator (e.g., local lab collection of samples).

6.5.4.1 Hematology

Hemoglobin, hematocrit, red blood cell count, white blood cell count with differential counts, and platelet count will be measured.

6.5.4.2 Clinical chemistry

Bilirubin (total, direct and indirect), alkaline phosphatase, AST (SGOT), ALT (SGPT), and GGT will be measured.

6.5.5 Electrocardiogram (ECG)

ECGs must be recorded as outlined in the central ECG reading manual. The preferred sequence of cardiovascular data collection during study visits is ECG collection first, followed by vital signs, and blood sampling. The Fridericia QT correction formula (QTcF) as reported by the central reader should be used for clinical decisions.

Single 12 lead ECGs are collected. The original ECGs, printed on non-heat sensitive paper, appropriately signed, must be collected and archived at the study site.

Each ECG tracing must be labeled with study number, patient initials, patient number, date and time, and filed in the study site source documents. For any ECGs with patient safety concerns, two additional ECGs must be performed to confirm the safety finding and forwarded to the central ECG laboratory for assessment. Clinically significant ECG findings at randomization (pre-dose) must be discussed with the sponsor before administration of study treatment.

Clinically significant abnormalities must be recorded on the relevant section of the medical history/Current medical conditions/AE eCRFs as appropriate.

6.5.6 Pregnancy and assessments of fertility

All pre-menopausal women who are not surgically sterile will have pregnancy testing. Serum pregnancy tests will be performed at the beginning and end of the study, with urine pregnancy tests performed at the remaining visits. The specific schedule is outlined in [Table 6-1](#) , [Table 6-2](#), [Table 6-3](#) , [Table 6-4](#) and [Table 6-5](#).

During COVID-19 pandemic, if a patient cannot visit the site to have pregnancy tests conducted the patient may complete a urine pregnancy test at home and report the result to the site. It is important that patients are instructed to perform the urine pregnancy test first and only if the test result is negative proceed with the administration of the study treatment. A communication process should be established with the patient so that the Site is informed of the pregnancy test results.

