5.5.4 Instructions for prescribing and taking study treatment

Subcutaneous (s.c.) injections are to be given for each investigational product administration. For purposes of study treatment dosing, “q.m.” refers to an every 4 weeks injection regimen. The study drug administration date should be in 4 week increments (+/- 5 days) from the first dose of study drug. Any dose administrations that may occur greater than +/- 5 days from the 4 week time point (e.g., patient unavailability) should be discussed with the Sponsor prior to dosing. The anatomical sites for administration of investigational product are the upper arm, upper thigh, or abdomen; the location of the injection sites should be documented in the source document.

Double-Blind Treatment Epoch:

Two injections of AMG 334 70 mg (equaling 140 mg total dose) or placebo will be administered by qualified study staff at each dosing visit during the 12-week double-blind treatment epoch (i.e., at Day 1 and Weeks 4 and 8).

Open-label Treatment Epoch and PTA-Open-Label Treatment Epoch:

Two injections of open-label AMG 334 70 mg (equaling 140 mg total dose) will be administered by qualified study staff at each dosing visit during the 156-week open-label treatment epoch (ie, at Weeks 12, 16, 20, 24, etc.) and during the PTA-Open-Label Treatment Epoch (ie, at Weeks 168, 172, 176, 180 etc.). If and when 140 mg/mL pre-filled syringes become available during the Open-Label Treatment Epoch, the 140 mg dose may be administered by a single 140 mg/mL s.c. injection.

The investigational product dose is fixed and will not be adjusted for individual patients during the study. There are no temporal restrictions for study drug administration (e.g., proximity to meals, sleep or activity).

All kits of study treatment assigned will be recorded in the IRT. Novartis monitors will reconcile treatment assigned vs treatment administered and ensure that the information is congruent during their monitoring visits.

During the **COVID-19 pandemic** that limits or prevents on-site study visits, delivery of study drug directly to a patient’s home is generally permitted in the event the Investigator has decided that an on-site visit by the patient is no longer appropriate or possible, and that it is in the interest of the patient’s health to administer (e.g., self-injection or study staff administration at patients’

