Serum Pregnancy	X					X			
Urine Pregnancy		X	X	X	X		X		
ECG	X		X	X		X			
Anti-AMG Antibodies			X			X	X		
eDiary Dispensing		S							
eDiary Return			S	S	S	S		Pt brings to each visit for use at site	
Clinical Outcomes (eDiary)		Daily (Migraine days, [REDACTED] duration, severity, rescue medication)							

Epoch	Screen	Baseline ³	Double-Blind Treatment ^{1,4}				Follow-Up ²	Notes
Visit	1	2	101	102	103	199	301	Follow up visit is 16 weeks after last dose of IMP (V103 / Wk 8), which is 12 weeks after last DBT visit (V199 / Wk 12).
Week	-6	-4	Day 1	4	8	12/PSD/TD	24/FU	
MPFID (eDiary)			Daily					
C-SSRS	X	X	X	X	X	X	X	Should also be performed at unscheduled visits.
Concomitant Medications	X	X	X	X	X	X	X	
Adverse Events ⁷			X	X	X	X	X	
Serious Adverse Events ⁷	X	X	X	X	X	X	X	
Study Drug Administration ⁸			X	X	X			
Contact IRT ⁹	X	X	X	X	X	X		
Screening Phase Completion Form	X							
Baseline Phase Completion Form		X						
Double Blind Phase Completion form						X		
Follow-Up Phase Completion Form							X	

1 – All study visit target dates are to be calculated from the Day 1 visit date, and all study procedures for a given visit should be completed in the same day.
 
2 – The Follow-Up Visit is required for all patients who either discontinue study drug early or complete the study in either the Double-Blind or Open-Label Treatment Epochs and do not continue commercial drug (if locally available).
 
3 – Enrollment into the Baseline Epoch can occur only if the patient successfully completes all requirements for the Screening Epoch.
								

Table 6-2 Assessment Schedule: Open-Label Treatment– Weeks 13-64 (1st year in Open-Label extension)

Epoch	Open-Label Treatment ^{1,2,3}													
	199	201	202	203	204	205	206	207	208	209	210	211	212	213
Visit														
Week	12	16	20	24	28	32	36	40	44	48	52	56	60	64
Open-label Treatment Phase Entry	X													
Complete Physical Exam	S													S
Brief Physical Exam		S	S	S	S	S	S	S	S	S	S	S	S	
Weight	X			X										X
Vital Signs ⁴	X	X	X	X	X	X	X	X	X	X	X	X	X	X
Chemistry/Hematology	X			X										X
Serum Pregnancy	X													X
Urine Pregnancy		X	X	X	X	X	X	X	X	X	X	X	X	
ECG	X	X												X
Anti-AMG Antibodies	X			X										X
eDiary Dispensing ⁵	S	S	S				S			S			S	
eDiary Return ⁵	S	S	S	S				S			S			S
Clinical Outcomes (eDiary) ⁶	Daily						X			X			X	
MPFID ^{6,9} (eDiary)	Daily						X			X			X	

Epoch	Open-Label Treatment ^{1,2,3}													
Visit	199	201	202	203	204	205	206	207	208	209	210	211	212	213

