Week	12	16	20	24	28	32	36	40	44	48	52	56	60	64
C-SSRS	X	X	X	X	X	X	X	X	X	X	X	X	X	X
Concomitant Medications	X	X	X	X	X	X	X	X	X	X	X	X	X	X
Adverse Events ¹⁰	X	X	X	X	X	X	X	X	X	X	X	X	X	X
Serious Adverse Events ¹⁰	X	X	X	X	X	X	X	X	X	X	X	X	X	X
Study Drug Administration ¹¹	X	X	X	X	X	X	X	X	X	X	X	X	X	X
Contact IRT ¹²	X	X	X	X	X	X	X	X	X	X	X	X	X	X

- 1 – All study visit target dates are to be calculated from the Day 1 visit date, and all study procedures for a given visit should be completed in the same day.
 2 – The Follow-Up Visit is required for all patients who either discontinue study drug early or complete the study and do not continue commercial drug (if locally available) in either the Double-Blind or Open-Label Treatment Epochs.
 3 – Entry into the Open-Label Treatment Epoch can occur only if the patient successfully completes all requirements for the Double-Blind Treatment Epoch.
 4 – Includes blood pressure, pulse and temperature.
 5 – eDiaries will be used for the first 12 weeks of the Open-Label Treatment Epoch and again at periodic intervals as identified in the assessment schedule.
 6 - Daily collection during the respective 4 week periods
 7 - HRQ collection after migraines during the respective 4 week periods

10 - SAEs will be collected after signing of the informed consent through the end of the Follow-Up Epoch end of study (16 weeks after the last dose of study drug). Non-serious AEs will be collected after randomization (Visit 101) through the end of the Follow-Up Epoch (16 weeks after the last dose of study drug).

11 – Two pre-filled syringes will be administered by study staff, during the applicable study visits, q.m., s.c..

12 - Sites will access the Interactive Response Technology (IRT) System to enter the patient into the open-label treatment phase and to register study early termination.

X = Assessment to be recorded in the source documents and the clinical data base; S = Assessment to be recorded as source documentation only.

Table 6-5 Assessment Schedule – PTA-Open-Label Treatment

Epoch		PTA Open-Label Treatment						499 ² / End PTA
		Initial 3 month cycle			Repeat 3-Month cycle until end of PTA			
Visit	299	401	402	403	404	405	406	
Weeks	168	172	176	180	184	188	192	
Study drug administration	X	X	X	X	X	X	X	
Contact IRT	X	X	X	X	X	X	X	
Adverse Events/ Serious Adverse Events	X	X	X	X	X	X	X	X
Concomitant medications / therapies	X	X	X	X	X	X	X	X
Clinical Global Impression - Severity	X							

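### At Visits 199 and 213 an open-label injection is paired with a serum-only pregnancy test, which conflicts with Section 6.5.6 and makes that visit's result unlikely to be known at dosing

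*Protocol*

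**What the plan says.** The rule on the type of test is in protocol Section 6.5.6: "Serum pregnancy tests will be performed at the beginning and end of the study, with urine pregnancy tests performed at the remaining visits". The same section refers to the assessment tables for the schedule.

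In Table 6-2, the row "Serum Pregnancy" is marked at V199 and V213 only. The row "Urine Pregnancy" is marked at V201 to V212 and is blank at V199 and V213. The row "Study Drug Administration" is marked at every visit in the table. Table 6-1 also shows serum alone at V199, and the SAP's copy (Table 14, Appendix D) agrees.

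Section 5.5.4 confirms the dosing sequence. Open-label injections are given "at each dosing visit during the 156-week open-label treatment epoch (ie, at Weeks 12, 16, 20, 24, etc". Week 64 falls in that four-weekly sequence.

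Two further statements bear on timing. Footnote 1 to Table 6-2 asks that "all study procedures for a given visit should be completed in the same day". Section 6.5.4 says: "A central laboratory will be used for analysis of all specimens collected". It leaves shipment and reporting to a laboratory manual.

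Section 3.6 says that women of child-bearing potential are screened for pregnancy at every study visit.

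**The concern.** At two of the open-label dosing visits the only scheduled pregnancy test is a sample that, on the face of Section 6.5.4, leaves the site for analysis, while the injection is due the same day. At the other dosing visits in Tables 6-1 and 6-2 the scheduled test is a urine test. The protocol does not explain the difference, and the wording of Section 6.5.6 does not support it for patients who continue.

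This is a question of patient safety and of internal consistency, not of the efficacy analysis. Section 3.6 says that endogenous CGRP may matter for fetoplacental development and fetal survival, and Section 5.6.2 makes pregnancy a mandatory reason to stop treatment. V199 deserves particular attention because it is the first AMG 334 dose for every continuing patient from the placebo arm.

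**Working it through.** The plan states no figure on this point, so the check is a reading of the tables followed by simple arithmetic.

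**Step 1. Tests and dosing, side by side**

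| Visit | Week | Serum | Urine | Study drug |
|---|---|---|---|---|
| 101–103 (Table 6-1) | Day 1, 4, 8 | – | X | X |
| 199 (Tables 6-1, 6-2) | 12 | X | – | X (Table 6-2) |
| 201–212 (Table 6-2) | 16–60 | – | X | X |
| 213 (Table 6-2) | 64 | X | – | X |
| 301 (Table 6-1) | 24/FU | – | X | – |

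Table 6-2 has 14 dosing visits: 12 with a urine test, 2 with serum only, 0 with both.

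**Step 2. Tables against Section 6.5.6**

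For a continuing patient V199 and V213 are followed by further dosing visits, so under the text they belong with the remaining visits and would carry urine. The tables give serum. The mismatch also runs the other way: V301, the last visit for a patient who stops after the double-blind epoch, carries urine rather than serum.

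**Step 3. Is the visit's result known at the injection?**

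The same-day footnote and the central-laboratory sentence together imply that it is not, if turnaround is one day or more. Turnaround is not stated and neither is the order of procedures within a visit. The result would be available only if the laboratory reported within the visit day, or if the site held the injection, which no section asks it to do.

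**Step 4. Age of the latest earlier scheduled result**

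- V199: (12 − 8) weeks × 7 = 28 days.
- V213: (64 − 60) weeks × 7 = 28 days.
- Section 5.5.4 allows ±5 days around each dosing date, so the gap can run from 28 − 10 = 18 to 28 + 10 = 38 days.

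**Step 5. How many patients**

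The Amendment 3 rationale reports that 240 patients continued into the open-label epoch. With 1:1 randomization and an assumed even split, 240 / 2 = 120 receive their first AMG 334 dose at V199.

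**Step 6. How many pregnancies could be affected**

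The number of women of child-bearing potential is not given. Exclusion criterion 20 requires highly effective contraception and mentions a failure rate below 1%, with no period stated. Taking this as an annual rate (assumption), the expected number over one 28-day gap is below n × 0.01 × 28/365:

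- Assumed share 40%: n = 96, giving 0.07.
- Assumed share 80%: n = 192, giving 0.15.
- Ceiling, all 240: 0.18.
- The half coming from placebo: 0.04 to 0.07, ceiling 0.09.

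Attendance at V213 is not given. It cannot exceed 240, so the ceiling of 0.18 also covers that visit.

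**The case against.** Several stronger readings are tempting, and the documents do not support them.

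- A reader might infer that these two doses are given before any pregnancy result is known. That is wrong: a urine result about 28 days old is scheduled before each. Only the visit's own result is in question.
- A reader might infer that the serum result cannot be available at dosing. No turnaround is stated and the laboratory manual is not in the documents. Unlikely is as far as the text goes.
- A reader might infer a breach of a stated rule, because Section 6.5.6 tells patients to "perform the urine pregnancy test first and only if the test result is negative proceed with the administration of the study treatment". That sentence covers home testing during the COVID-19 pandemic. No section sets such a condition for on-site visits. Nor is a test before every dose a protocol-wide pattern: Table 6-5 marks drug at V299, 401, 402, 404 and 405 with no pregnancy test in that table.
- A reader might count every woman dosed at V199 as harmed or exposed in pregnancy. Such a count rests on an assumed share and measures doses, not pregnancies. With mandatory contraception the expected number is a fraction of one.

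Two further objections carry weight. First, taken literally the central-laboratory sentence covers urine as well as serum, while the subsections of 6.5.4 list only hematology and chemistry. The contrast between a urine test read on site and serum sent away is therefore partly inference. It is a reasonable one: Section 6.5.6 lets patients read a urine test at home and report it, and Table 6-5 has urine results documented in source documents. Second, the end of the study in Section 6.5.6 may have been meant loosely as the end of an epoch. The amendment log notes that V213 was once V299, the final open-label visit, which would explain the pattern. It would not explain why a visit that now includes dosing keeps it without comment.

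Finally, enrollment ended in July 2017 and the current protocol cites a February 2020 Investigator Brochure, so both visits have almost certainly passed. That limits the practical effect of an edit but does not remove the inconsistency.

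**Conclusion.** The point holds in a limited form. Two of the 14 dosing visits in Table 6-2 carry a serum pregnancy test without urine, contrary to the wording of Section 6.5.6 for a continuing patient. At those visits the test result is unlikely to be known when the injection is given.

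The first part is a plain reading of the documents. The second is an inference that depends on serum samples going to the central laboratory and on turnaround exceeding the visit day. The earlier result is nominally 28 days old. At V199 about 120 patients receive AMG 334 for the first time; at V213 that consideration does not apply, because continuing patients have already had about a year of open-label drug.

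The expected number of exposed pregnancies is small: below about 0.2 at either visit, assuming the stated failure rate is annual and contraception is used as required. The point still merits correction because it concerns patient safety and the discrepancy is unexplained.

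Tables 6-3 and 6-4 are not in the text available for this review, so later year-end visits, and any repeat of V213 with further tests, could not be checked.

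**What to change.** The sponsor should reconcile Tables 6-1 and 6-2 with Sections 3.6, 6.5.4 and 6.5.6. The type of pregnancy test at V199 and V213, and its timing relative to the injection, should either be consistent with the other dosing visits in those tables or differ for a stated reason. Section 6.5.6 should make clear which visits count as the beginning and end of the study, and Section 6.5.4 should make clear whether pregnancy samples fall under the central-laboratory statement. The choice of clinical rule is for the sponsor.

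Tables 6-3 and 6-4 should be checked for the same pattern. As V199 and V213 have probably been completed, it would also help to record how the result and the injection were ordered in practice.

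The cost is a small edit to two tables and one or two sentences, with the SAP's copy of Table 6-1 (Table 14) brought into line if that table changes. No endpoint, sample size or analysis is affected.
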